Spinal Cord Injury Program in Exercise (SCIPE)

NCT03925077

Study Protocol

July 22nd, 2023

Checklist for SCiPE Participant Screening to Enrollment

Once a potential participant completes the SCiPE study *F01 Pre-screening Form (F01 Form, Application)* through the screening website, the pre-screening data will be automatically fetched to an inactive arm (Arm 2) of the study database (REDCap SCiPE) if the potential participant is eligible based on the **age** and **SCI diagnosis criteria**. **If a potential participant made a wrong entry in the *F01 Form* and was rejected to be part of the study, See Appendix II.**

Screening website - <https://screen.scipe.org/#/apply>

REDCap link- <https://redcap.dom.uab.edu/index.php?action=myprojects>

All data fetched to the Arm 2 will go through automatic duplicate checks to ensure that each individual has only one study ID. The duplicate check is performed based on the following rules: **Name** (first and last) and **Phone Number**. IDs that are identified as duplicates will remain in the Arm 2. Non-duplicate IDs and associated data will be transferred to active arm (Arm 1) in REDCap. All data moved to the Arm 1 will be automatically saved. This fetching, duplication check, and the saving process happen daily at a scheduled time (every 30 min) using a computer-generated script.

Once an ID with the fetched data is automatically saved under *F01 Form* in REDCap (status remains as incomplete, RED), it will trigger an automatic survey invitation and sent out *F02 Screening Interview Form (F02 Form)* to that individual. The *F02 Form* includes question items to obtain personal information, PAR-Q+, and secondary contact information. **We can manually check whether or not the invitation was sent in two places (See Appendix III).**

Recruitment Coordinator should check the study database daily to:

- 1) Ensure that data is fetched to REDCap (Step 1);
- 2) Monitor completion of the *F02 Form* (Step 2 – 6);
- 3) Identify individuals who need medical clearance, obtain one when necessary, and ensure individuals' mailing addresses (Step 7 – 11); and
- 4) Monitor completion of the consenting process (Step 12 – 17).

Please check each step below to complete the screening to enrollment process.

Please ensure all phone calls are documented using the *Call Log* in REDCap.

Step	✓	Description
1		
When a new user applies for the study, an email notification, Application Received, will be sent to the study email ([contact]).
 
Check the most recent email, Application Received, and ensure that the data is fetched to REDCap F01 Pre-Screening using the email address. This auto fetching/saving process happens daily, every 30 minutes (e.g., 10:00 am, 10:30 am, 11:00 am).
 
If the auto fetching/saving process does not occur, inform Data Team. Note that the UAB server reboots and disables the auto-transcript every 2nd Wednesday of the month.
 
Check all F01 Pre-Screening forms that contain the fetched data for any missingness. If not missing data identified, Save and Exit Form as Complete.

2	
The auto invitation of the F02 Form is set to send up to 3 times, every 3 days:
 
 1) The initial F02 Form is sent immediately after the F01 Form is automatically saved. No action is required. 2) When the initial F02 Form is not completed by the potential participant within 3 days (3 days from the initial F02 Form), a second F02 Form will be sent automatically from REDCap. No action is required. 3) When the second F02 Form is not completed by the potential participant after 3 days (6 days from the initial F02 Form), a third F02 Form will be sent automatically from REDCap. 
If the potential participant completes the F02 Form before the third invitation, continue with Step 7.
 
If the potential participant did not complete the F02 Form and the third invitation is sent, an email notification, Incomplete Screening Form, will be sent to the study email. Continue with Step 3.

3	
Go to REDCap and call the potential participant using the phone number stored under the F01 Form. Contact him/her at preferred contact time. Record the phone call/attempts using the Call Log in REDCap.
 
If the potential participant responds to the phone call, inform him/her that you sent the F02 Form again and ask to complete it within the next 3 days.
 
If the potential participant does not respond to the phone call, leave a voice message and email to inform him/her that you sent the F02 Form again and ask to complete it within the next 3 days.

4	
If the potential participant completes the F02 Form within 3 days, continue with Step 7.

5	
If the potential participant did not complete the F02 Form within 3 days after the phone call (9 days from the initial F02 Form), an email notification, Incomplete Screening Form, will be sent out to the study email. Continue with Step 6.

6	
Under the Lost to Contact/Withdrawn Form in REDCap, mark the person as Unable to reach and indicate the Date and when the Unable to reach was determined during the study period (Before screening). No further action is required after the potential participant is marked as Unable to reach.

7	
Go to Record Status Dashboard on the left panel in REDCap and select the display option: Medical Clearance Upload Needed from the Dashboard Displayed dropdown list. This dashboard provides a list of potential participants who need medical clearance before enrolling in the SCiPE study. Continue with Step 8.
 
An email notification will also be sent to the study email if the potential participant needs medical clearance, as identified in REDCap.

8	
The Recruitment Coordinator should ensure that the potential participant met the eligibility prior to calling him/her for medical clearance. Indicating whether a potential participant is eligible or not is done by completing the 1st question under the Medical Clearance Form as below:

	
“Is the participant eligible for the study based on the screening?”
 
Under this question are self-reported age, presence of spinal cord injury, and current pregnancy from F02 Form completed by the potential participant. Eligibility is determined by three criteria: 1) between the ages of 18 to 65, 2) presence of spinal cord injury, and 3) not currently pregnant.
 
Go to REDCap and call the potential participant using the phone number stored under the F01 Form. Contact him/her at preferred contact time. Record the phone call/ attempt using the Call Log in REDCap.
 
Group 1: Ineligible, Yes for medical clearance
 
** A total of 3 call attempts should be made with each being at least 3 days apart if the potential participant cannot be reached.
 
** If the potential participant cannot be reached this time, please make sure to exit the Medical Clearance Form by clicking the Cancel button at the end of the form, which will ensure the form status remains as No Color (Incomplete or Red status indicates a person is ineligible).
 
(1) Eligibility
 
If the potential participant is outside of the age range, confirm the reported Date of Birth is accurate. If the Date of Birth is inaccurate, correct the information under F02 Form. Once the potential participant is determined as eligible, check Yes and obtain physician contact information.
 
If the potential participant does not respond 3 days after the 3rd call attempt, please assume the reported Date of Birth is accurate. Check No and Save and Exit Form as Incomplete. No further action is required at this point.
 
(2) Physical, mailing address
 
If the potential participant is determined as eligible, check and confirm the potential participant's mailing address for future equipment shipping. If change is needed, revise the address fields under the F02 Form.
 
Indicate whether or not the participant's mailing address has confirmed (yes/no). This question is located in the F02 Form as below:
 
“Participant’s mailing address has been confirmed during the process of obtaining physician’s contact information”
 
(3) Obtain physician contact Information (see Appendix I for script to obtain physician contact information)
 
Record the physician contact information under the Medical Clearance Form in REDCap.
 
Group 2: Eligible, Yes for medical clearance
 
** A total of 3 phone calls should be made with each being at least 3 days apart if the potential participant cannot be reached.

--	--

	
** If the potential participant cannot be reached this time, please make sure to exit the Medical Clearance Form by clicking the Cancel button at the end of the form, which will ensure the form status remains as No Color (Incomplete or Red status indicates a person is ineligible).
 
(1) Eligibility
 
If the potential participant meets the three eligibility criteria, check Yes and continue with obtaining physician contact information.
 
If the potential participant does not respond 3 days after the 3rd phone call, Save and Exit Form as Incomplete. Continue with Step 15.
 
(2) Physical, mailing address
 
Check and confirm the potential participant's mailing address for future equipment shipping. If change is needed, revise the address fields under the F02 Form.
 
Indicate whether or not the participant's mailing address has confirmed (yes/no). This question is located in the F02 Form as below:
 
"Participant's mailing address has been confirmed during the process of obtaining physician's contact information"
 
(3) Obtain physician contact Information (See Appendix I for script to obtain physician contact information)
 
Record the physician contact information under the Medical Clearance Form in REDCap.

9	
Begin the physician clearance process.
 
Fax the Fax Cover Page and Statement of Medical Clearance for Exercise to the potential participant's physician using the contact information obtained during Step 8.

	
File the faxed documents in a secure cabinet until completed and signed Statement of Medical Clearance for Exercise arrives.

	
Go to the Medical Clearance Form in REDCap.
 
Enter the date when the first fax was sent, and change the form status to Unverified. This marks the potential participants who are in the process of obtaining medical clearance as a yellow color.

10	
After receiving the completed Statement of Medical Clearance for Exercise, conceal all participant information and scan the document. Upload the scanned form to REDCap to the "Upload the signed medical clearance form" section under the Medical Clearance Form.
 
Shred the paper copy and mark the form status as Complete and save the record. This will trigger the auto invitation of the e-Consent Form (Initial). Continue with Step 11.

11	
Upon completion of reaching out to potential participants who need medical clearance, change the display option of the Record Status Dashboard to the Default Dashboard.

	
Identify potential participants who do not need medical clearance (F02 Form has Complete status and is shown as Green & Medical Clearance Form is shown with No Color).
 
The Recruitment Coordinator should ensure the potential participant met the eligibility prior to a follow-up phone call. Go to the Medical Clearance Form and indicate whether the potential participant is eligible or not by completing the 1st question under the Medical Clearance Form as below:
 
“Is the participant eligible for the study based on the screening?”
 
Under this question are self-reported age, presence of spinal cord injury, and current pregnancy from F02 Form completed by the potential participant. Eligibility is determined by three criteria: 1) between the ages of 18 to 65, 2) presence of spinal cord injury, and 3) not currently pregnant.
 
Go to REDCap and call the potential participant using the phone number stored under the F01 Form. Contact him/her at preferred contact time. Record the phone call/ attempt using the Call Log in REDCap.
 
Group 3: Ineligible, No medical clearance
 
**A total of 3 call attempts should be made with each being at least 3 days apart if the potential participant cannot be reached.
 
** If the potential participant cannot be reached this time, please make sure to exit the Medical Clearance Form by clicking the Cancel button at the end of the form, which will ensure the form status remains as No Color (Incomplete or Red status indicates a person is ineligible).
 
(1) Eligibility
 
If the potential participant is outside of the age range, confirm the reported Date of Birth is accurate. If the Date of Birth is inaccurate, correct the information under F02 Form. Once the potential participant is determined as eligible, check Yes and mark the status as Complete and save. This will immediately trigger e-Consent Form (initial) via REDCap. Continue with Step 12.
 
If the potential participant does not respond 3 days after the 3rd call attempt, please assume the reported Date of Birth is accurate. Check No and Save and Exit Form as Incomplete. No further action is required at this point.
 
(2) Physical, mailing address
 
If the potential participant is determined as eligible, check and confirm the potential participant's mailing address for future equipment shipping. If change is needed, revise the address fields under the F02 Form.
 
Indicate whether or not the participant's mailing address has confirmed (yes/no). This question is located in the F02 Form as below:
 
“Participant’s mailing address has been confirmed during the process of obtaining physician’s contact information”
 
Group 4: Eligible, No medical clearance

--	--

		If the potential participant meets the three eligibility criteria, check Yes and mark the status as Complete and Save and Exit Form. This will immediately trigger e-Consent Form (initial) via REDCap. Continue with Step 12 .
12	√	
The auto invitation of the e-Consent Form is set to send up to 3 times with each being 3 days apart:
 
 1) The initial e-Consent Form is sent after the F02 Form and Medical clearance Form are marked as Complete. No action is required. 2) When the initial e-Consent Form is not completed by the potential participant after 3 days (3 days from the initial e-Consent Form), a second e-Consent Form will be sent automatically from REDCap. No action is required. 3) When the second e-Consent Form is not completed by the potential participant after 3 days (6 days from the initial e-Consent Form), a third e-Consent Form will be sent automatically from REDCap. 
If the potential participant completes the e-Consent Form before the third invitation, continue with Step 16.
 
If the potential participant did not complete the e-Consent Form and the third invitation is sent, an email notification, Incomplete eConsent Form, will be sent to the study email. Continue with Step 13.

13		
Go to REDCap and call the potential participant using the phone number stored under the F01 Form. Contact him/her at preferred contact time. Record the phone call/attempts using the Call Log in REDCap.
 
If the potential participant responds to the phone call, inform him/her that the e-Consent Form has been sent again and ask to complete it within the next 3 days.
 
If the potential participant does not respond to the phone call, leave voice message and email to inform him/her that the e-Consent Form has been sent again and ask to complete it within the next 3 days.

14		
If the potential participant completes the e-Consent Form within 3 days, continue with Step 16.

14		
If the potential participant did not complete the e-Consent Form within 3 days after the phone call (9 days from the initial e-Consent Form), an email notification, Incomplete e-Consent Form, will be sent out to the study email. Continue with Step 15.

15		
Under the Lost to Contact/Withdrawn Form in REDCap, mark the person as Unable to reach and indicate the Date and when the Unable to reach was determined during the study period (Post screening). No further action is required after the potential participant is marked as Unable to reach.

16	√	
The potential participant is officially enrolled in the study upon completion of the e-Consent Form. A baseline questionnaire packet will be automatically emailed to the participant via REDCap. No additional action is required.

Participant ID: _____
Staff ID: _____

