Appendix I. Telephone Script for Obtaining Physician Clearance

Hi, my name is _____. I'm calling from the SCiPE Study at UAB. Thank you for answering our questions regarding your health. Based on the information you provided, you are eligible to participate in our study. In order for you to participate in the study, we will need to complete some additional paperwork. First, can I have your physician contact information? We will fax him/her to make sure that they feel this study is a good fit for you. Once we receive your medical clearance, we will contact you again and email you a consent form to complete the enrollment process.

Mailing address check.

Do you have any questions at this time?

We appreciate your time and interest in this study. We will be in touch as soon as we complete the medical clearance process.

Appendix II. When a potential participant made a wrong entry in the F01 Form and was rejected to be part of the study

1. Login to the app.scipe.org as admin;
2. Go to the *User Management* option under *Content Management* section;
3. Find the rejected user using his/her email address;
4. Click the **edit icon** in the first column of the user to enter the record;
5. Under Status, change the user's status by typing **application-pending** (*No manual data correction)
6. Click **Edit** on the bottom of the page and finish the process
7. No further action is needed. The user's data will be fetched to Arm 2 in REDCap when the next run of fetching occurs.

Ensure to record communication in REDCap using the Other category of the Call Log. Under the Note section, please record the purpose of this call was for change of the user status due to (1) age range or (2) presence of SCI.

Participant ID: _____
 Staff ID: _____

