	
are just checking to make sure everything is ok since he/she hasn't been on the website for past 3 weeks. Encourage him/her to watch and exercise three times per week;
 
 If the participant does not respond to the phone call, leave a voice message and inform him/her that you are just checking to make sure everything is ok since he/she hasn't been on the website for 3 weeks. Encourage him/her to watch and exercise three times per week. If the same participant shows up in the report again the week after (4th) week, please go to Packet 2 (if SET) or Packet 2-1 (if Control) of that participant and check the the date when the survey will be sent via the Invitation Status icon. Put the date on your calendar as a reminder for the 3rd Call. Under the Lost to Contact/Withdrawn Form in REDCap, mark the person as Lost to Contact and indicate the date when the lost to contact was determined during the study period (During intervention). This will remove the participant from the Adherence Report. 
 Record this 2nd call attempt using the Adherence Call section under the Call Log in REDCap. Third Call: Call the participant on the date when the Packet 2 or Packet 2-1 is scheduled to send. If the participant responds to the phone call, inform him/her that the post-intervention questionnaire packet has been sent and ask him/her to complete in order to receive the gift card. 
 If the participant does not respond to the phone call, leave a voice message and inform him/her that the post-intervention questionnaire packet (Packet 2 or 2-1) has been sent and ask him/her to complete in order to receive the gift card. If the participant completes Packet 2 or 2-1, remove him/her from the Lost to Contact status under the Lost to Contact/Withdrawn Form in REDCap If the participant does not respond to the phone call and does not complete Packet 2 or 2-1, his/her Lost to Contact status remains. Record this 3rd call attempt using the Adherence Call section under the Call Log in REDCap.
--	--

Check Completion Status of Post-Intervention, 12-Week, and 16-Week Assessments:

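### The one-ID-per-person check matches only name and phone, leaves the match rule unstated, and is not described again before randomisation, so a repeat applicant could be randomised twice.

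*Combined protocol and SAP*

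**What the plan says.** The opening text of the Checklist for SCiPE Participant Screening to Enrollment sets the purpose of the check: to "ensure that each individual has only one study ID". Applications that pass on age and spinal cord injury "will be automatically fetched to an inactive arm (Arm 2) of the study database". (This is a holding area in REDCap, not a treatment arm.) There, "All data fetched to the Arm 2 will go through automatic duplicate checks", in a run every 30 minutes. "The duplicate check is performed based on the following rules": name (first and last) and phone number. Records not flagged move to the active database arm. For the rest, "IDs that are identified as duplicates will remain in the Arm 2".

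Other relevant places:

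- **Step 1 of the screening checklist:** email is already used to find the fetched F01 record.
- **Steps 8 and 11 of the screening checklist:** eligibility is judged on self-reported age, injury and pregnancy. Date of birth and mailing address are on the F02 Form. A physician's statement is sought only for those flagged for medical clearance.
- **Perform Randomization, Step 5:** staff press the button and confirm. No identity check is described.
- **Adherence monitoring, Third Call:** staff mention the post-intervention packet and "ask him/her to complete in order to receive the gift card".
- **Statistical analysis, both phases:** data are screened for errors, missingness and normality. Duplicates are not named. Participant is the random effect.

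**The concern.** The check has a clear aim, but its two keys are easily changed and it is placed before the stronger identifiers arrive. A person with two phone numbers, or who uses a nickname, may look new to the script. Nothing later in the available text is described as a test of whether the person is already enrolled.

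If one person holds two IDs, three things can go wrong. The two records are correlated, but a random effect indexed by study ID treats them as independent. If they fall in different arms, the person has access to both programmes and the contrast is contaminated. And the reported number of participants is too high. Enrolment and questionnaires are remote and a gift card rewards completion, so the possibility deserves a deliberate check.

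**Working it through.** The plan gives no duplicate rate and no figure to reproduce. The main check is a reading of the text; the arithmetic only sets a scale.

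**1. What it takes to pass the check.** The keys are listed as rules joined by a conjunction, with no statement of how they combine.

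| Reading | A repeat applicant passes by changing | Side effect |
|---|---|---|
| Both keys must match | Either the name form or the phone | Few false flags |
| One match is enough | Both the name form and the phone | People sharing a phone or a name are held back |

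Under the second reading the side effect matters, because no review of held records is described.

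**2. Where the check could be repeated.**

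| Stage | Identifiers held | Identity check described? |
|---|---|---|
| F01 fetch | Name, phone, email | Yes, on name and phone |
| F02 Form | Adds date of birth and mailing address | No |
| Medical clearance, e-consent, Packet 1 | As above | No |
| Randomisation | As above | No |
| Analysis | As above | Not named |

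**3. Incidental exposure.** Equipment is shipped only to the SET arm, and the Control shipping form is closed empty. Two SET allocations could show up as two parcels to one address. A person in both arms generates one parcel, so the more damaging case gives no signal there.

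**4. Scale.** The only size stated is 36, for the pilot phase. The following are assumptions: the 36 are records, 18 per arm, independent 1:1 allocation, and a within-person correlation ρ of 0.5 to 1.0 between the two records.

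- Share of records held by one duplicated person: 2/36 = 5.6%. The surplus alone is 1/36 = 2.8%.
- With d duplicated people and both records of each in the same arm, the true variance of the difference in means divided by the naive variance is 1 + dρ/18. For d = 1 this is 1 + 0.5/18 = 1.028 to 1 + 1/18 = 1.056. For d = 3 it is 1.083 to 1.167.
- With every pair split across arms, the ratio is 1 − dρ/18: 0.972 to 0.944 for d = 1. The naive variance is then slightly too large, and the harm is contamination rather than false precision.
- Chance that at least one pair is split: 1 − 0.5^d, which is 50% for d = 1, 75% for d = 2 and 87.5% for d = 3.

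**5. Rejected applications.** These are not fetched, so a later application with a changed age or injury answer is not automatically compared with the rejected attempt. The documented route for a wrong entry, Appendix II, asks staff to log the reason for the status change. A fresh application would leave no such log.

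**The case against.** The strongest case against is that the text supports less than a reader might infer.

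- **That the check runs only on a person's first application.** It does not. Every fetched record is checked, including a repeat application. A rejected one that staff reset is covered too: "The user's data will be fetched to Arm 2 in REDCap when the next run of fetching occurs". The limit is the stage, F01, not the attempt.
- **That changing one field always gets through.** This is true only if both keys must match, which is not stated. Likewise, blocking of household members arises only if one match is enough. Both faults cannot hold together.
- **That leaving out rejected applications leads to double randomisation.** It cannot, because a rejected application is never randomised. Rejected users also stay in the website's user list, where staff can find them by email. What is missing is an automatic link.
- **That Group 4 applicants get no personal contact.** The Group 4 text says only that a person who "meets the three eligibility criteria, check Yes and mark the status as Complete and Save and Exit Form" proceeds to consent. But the common part of Step 11, placed before the groups, tells the coordinator to call. This is unclear at most.
- **That the website reveals the allocation.** Staff choose a user type and the participant receives a link. What the participant is told is not stated.

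It can also be said that a second gift card takes real effort: another consent, another baseline packet and a packet sent 58 days after randomisation. The Step 1 lookup by email might bring a wrongly held applicant to light. Both analysis sections are in the past tense, so for those data only a retrospective search helps. Some text between Appendix II and the baseline checklist is not available here, and a further check in it cannot be excluded.

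These points narrow the concern but do not remove it. The calls, lookups and shipping might expose a duplicate by chance; none is described as a duplicate check.

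**Conclusion.** The point holds as a cheap improvement. The stated aim is one ID per individual. The stated method uses two changeable keys with an unstated combination rule, at one stage, and does not use identifiers the study already holds. A person who changes one field (if both must match) or both fields (if either is enough) could be randomised twice, and the model would treat the two IDs as different people.

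The size is unknown, and the documents give no evidence that any duplicate occurred; a reader should not infer one. For scale, one duplicated person would hold 5.6% of 36 pilot records, with about an even chance of being in both arms. The variance effect of one same-arm pair is small, about 3% to 6% under the assumptions above. No size is stated for the feasibility phase, so no share can be given there. The missing link to rejected applications is a separate and lesser matter: it concerns the reliability of self-reported eligibility, not double randomisation.

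**What to change.** 1. State how the name and phone rules combine.
2. Add email as a key at F01, and date of birth together with mailing address once F02 is complete.
3. Re-run the check after F02 and before the Randomize button is pressed.
4. Have the Recruitment Coordinator resolve flagged records by phone and log the outcome, instead of leaving them in the inactive database arm.
5. Include rejected applications in the comparison, to flag changed age or injury answers.
6. Run the rule once on all existing records in both phases and report the number found, even if it is zero. If any are found, repeat the analysis with only the first record per person. Say also whether the person was in both arms, since dropping the second record does not undo exposure to the other programme.

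The cost is a script change, one retrospective search and occasional manual review. The downside is a few false matches, such as members of one household, to clear by phone. The retrospective search is worth doing even if recruitment has ended, because it replaces an unknown with a number that can be reported.

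### Step 11's colour rule for applicants who need no medical clearance also picks up applicants who need it but have not been reached, so e-Consent could go out without clearance

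*Combined protocol and SAP*

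**What the plan says.** The screening-to-enrolment checklist sorts applicants by eligibility and by need for medical clearance. Step 8 handles those flagged as needing it: "Group 1: Ineligible, Yes for medical clearance" and "Group 2: Eligible, Yes for medical clearance". For Group 2, "A total of 3 phone calls should be made with each being at least 3 days apart"; Group 1 has the same spacing. In both groups, staff who cannot reach the applicant must leave the Medical Clearance Form by Cancel so that it keeps no colour. The form is saved as Incomplete only when there is still no response 3 days after the third call. It turns yellow at Step 9, once the clearance request has been faxed.

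Step 11 handles the rest. It begins "Upon completion of reaching out to potential participants who need medical clearance", moves the display back to the default dashboard, and instructs staff to "Identify potential participants who do not need medical clearance". The test in brackets is that F02 is Complete (Green) and the Medical Clearance Form "is shown with No Color". It adds: "The Recruitment Coordinator should ensure the potential participant met the eligibility prior to a follow-up phone call". Group 4 (eligible) is marked Complete on the three eligibility criteria. For Group 3, after a date-of-birth correction, "Once the potential participant is determined as eligible, check Yes and mark the status as Complete and save". Either action releases e-Consent at once. Step 12 describes the trigger as both forms being Complete.

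**The concern.** The checklist treats clearance as a gate. The Step 7 dashboard lists people who must have it before enrolment, and the Appendix I script says the consent form follows receipt of clearance. If the Step 11 test cannot tell a flagged applicant from an unflagged one, the gate depends on the coordinator noticing something that Step 11 does not ask for.

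Completing e-Consent is enrolment (Step 16). A flagged person released in error who then completes Packet 1 could be randomised and given website access uncleared. SET participants also receive wrist weights. Exposure is not shown to be confined to SET: in the second checklist, controls also get website access (Step 8), and the adherence calls that encourage exercise cover them (Step 11). The stake is participant safety, not the estimate of effect.

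**Working it through.** The plan gives no figure to reproduce. The check traces form status and then counts days.

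**Status trace (Steps 7 to 12).** Applicants get to Step 7 only after completing F02, so F02 is Green in every row.

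| Applicant | Needs clearance? | Medical Clearance Form | Meets Step 11 test? |
|---|---|---|---|
| Group 1, not yet reached | Yes | No colour (Step 8, Cancel) | Yes |
| Group 2, not yet reached | Yes | No colour (Step 8, Cancel) | Yes |
| Groups 3 and 4, not yet processed | No | No colour | Yes, as intended |
| Flagged, fax sent | Yes | Yellow (Step 9) | No |
| Flagged, three failed calls plus 3 days | Yes | Incomplete/Red (Step 8) | No |

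The test therefore does not separate Group 2 from Group 4, or Group 1 from Group 3. For Group 2 the route to release is direct, because its members meet the same three criteria as Group 4 and need for clearance is not one of them. For Group 1 it is conditional: the person must be reached and a wrong date of birth corrected into range.

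**Minimum time in the overlap.** Inputs from Step 8: three calls at least 3 days apart, and the form set to Incomplete 3 days after the third.

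- Call 1 = day 0; call 2 ≥ day 3; call 3 ≥ day 6.
- Never reached: at least 6 + 3 = 9 days without colour.
- Reached on call 2 or call 3: at least 3 or 6 days up to the contact, and longer if the form is not saved until the fax.

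**Number of checks.** The introduction to the checklist requires a daily database check. Assume Step 11 is run after Step 8 at each one.

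- Every calendar day, days 0 to 8: 9 checks.
- Calls and checks on Monday to Friday only, with each due date that falls on a weekend moved to Monday:

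| Call 1 | Call 2 | Call 3 | Set to Incomplete | Checks before that |
|---|---|---|---|---|
| Mon | Thu | Mon | Thu | 5 + 3 = 8 |
| Tue | Fri | Mon | Thu | 4 + 3 = 7 |
| Wed | Mon | Thu | Mon | 3 + 5 = 8 |
| Thu | Mon | Thu | Mon | 2 + 5 = 7 |
| Fri | Mon | Thu | Mon | 1 + 5 = 6 |

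The minimum is 6. Each applicant can be misprocessed at most once, so these are opportunities and not expected errors.

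**Later checks.** After release, the available checklist steps mention clearance twice: Step 12 (form marked Complete) and Step 6 of the second checklist (mailing address only). Neither looks for the uploaded clearance.

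**The case against.** The strongest reply is that Step 11 does not direct anyone to release a flagged applicant. Its stated aim is people who need no clearance, and its only branches are headed as such. Marking a Group 2 applicant Complete would contradict both. The coordinator has also just worked the Step 7 dashboard, received an email about the flagged person, and logged a call. This stands as a reason why the error is avoidable. However, Step 11 moves away from that dashboard, requires none of these as a cross-check, and does not make the Group 4 action depend on the call or the log.

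The second reply is step order. If the opening condition means that every call attempt is finished, or if the sheet is kept per participant (it carries a Participant ID), no flagged applicant is still without colour when Step 11 is reached. That reading is possible and would remove the overlap, but the text does not state it. Checks are daily, Step 11 selects people in the plural from a dashboard, and Step 10 sends staff on to Step 11 after a single clearance. All of this fits rolling use better.

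Third, the REDCap trigger logic is not shown, and the part of the document between Appendix II and the second checklist's Step 1 was not available. The trigger may already require the upload, and the count of later checks is incomplete to that extent. This limits confidence but does not repair the written rule.

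Finally, the Week 8 analyses of both phases are written in the past tense, so new wording may help few people. That is right as far as wording goes; for records already processed, only a retrospective report helps.

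**Conclusion.** The concern holds. As written, the only operational test in Step 11 also matches flagged applicants who have not been reached, and the actions that follow can release e-Consent without clearance. The overlap lasts at least 9 days for someone never reached. That gives at least 9 calendar-day checks, or 6 to 8 on the minimum working-day schedule, if Step 11 is run daily after Step 8. Frequency cannot be derived: the documents give neither the share flagged, nor the share missed on the first call, nor any misprocessing rate. Nothing shows that a lapse occurred. The conclusion rests on rolling use of the checklist and on a trigger that works as Step 12 describes. It should be fixed, with medium confidence that the gap existed in practice.

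**What to change.** In Step 11, select applicants whose F02 is Complete, whose Medical Clearance Form has no colour, and who are not on the *Medical Clearance Upload Needed* dashboard. Confirm that the e-Consent trigger requires the uploaded clearance file when the flag is set, and add that condition if it does not. For records already processed, run one REDCap report covering both arms: flagged as needing clearance, form Complete, no file uploaded. This shows whether the lapse ever occurred.

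The cost is one sentence, one check of the trigger (with one added condition if needed) and one report. The downside is that e-Consent may arrive later for a few applicants.
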